we will collect fasting blood samples to measure HbA1c and will also store additional serum/plasma, whole blood aliquots and buffy coats at -80°C for future analyses, including measurement of glucose, insulin and lipids, and potential future metabolomics or genetic analyses. Details of the blood sample collection are shown in **Table 4**. In the event that a participant moves, we may request that they collect a fasting blood sample at a local LabCorp and we will measure HbA1c, glucose, insulin, and lipids at the 3 and 6-month visits. HOMA-IR will be calculated from fasting glucose and insulin.

HbA1c will be measured at LabCorp (Roche Tina Quant; fresh samples) from whole blood collected at screening, 3-month, and 6-month visits. Following trial completion, to improve precision of HbA1c estimates, HbA1c will also be measured at the Diabetes Diagnostic Laboratory (ion-exchange method; Tosoh G8 HPLC Analyzer; frozen samples) from whole blood collected at randomization, 3-month, and 6-month visits. Samples with Hb variants (C, D, E, S) that are measured at the Diabetes Diagnostic Laboratory will be reflexed for measurement by boronate affinity HPLC (Trinity Premier Hb9210).¹¹³

Table 4. Study visit schedule for specimen collection

	SV	RZ	3 month	6 month TV
HbA1c	X		X	X
Serum creatinine	X			
Hemoglobin	X			
Storage of aliquots and buffy coats (for measurement of glucose, insulin, lipids, other potential future measurements)		X	X	X
Urine sample for pregnancy	X			
Urine sample for ketones and other markers		X	X	X
Stool sample		X	X	X
CGM				X

10.B.6. Urine collection: Study staff will collect spot urine specimens at RZ, interim visit, and the final visit to measure ketones.

10.B.7. Stool Specimen Collection: Stool samples will be collected from all eligible and willing trial participants during the RZ, 3-month, and 6-month TV, following the protocol set forth by the Human Microbiome Project.^{114,115} Participants will be given a stool collection kit, which includes the specimen collection container, a shipper for home collection, and a form to record the timing and pertinent information related to specimen collection. Participants will be instructed to return the kit to the clinic within two days of collection (in-person or via shipping), at which time stool samples are stored at -80°C until analyses. Kits and instructions for collection will be reviewed by study staff with the participant at the required visits.

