13.B.1. Exploratory data analysis: We will express group data for variables with a normal distribution as mean \pm standard deviation and for variables not normally distributed as median and interquartile ranges (or will log-transform the variables to obtain a normal distribution). We will compare means and percentages of baseline variables across the intervention and usual diet group to assess similarity of these groups at randomization.

13.B.2. Primary, secondary, and exploratory outcomes: We will test the primary study hypothesis that there is a greater reduction in HbA1c from baseline to 6 months in the intervention group than in the usual diet group. To do this, we will use linear regression with change in HbA1c from baseline to 6 months as the dependent variable

We will use Bland-Altman plots to explore whether there is a systematic difference in HbA1c measured by LabCorp compared with DDL. If there is not a systematic difference in HbA1c measured at these two laboratories, to improve precision in the estimate of the primary outcome (difference in change in HbA1c between the intervention and control groups), we will use the weighted average of change in HbA1c measures from the two labs as the outcome (weights defined as the ratio of the variance for each lab over the sum of the variance) (50). If we observe a systematic difference between HbA1c measured at LabCorp and DDL, we will use HbA1c measured at DDL.

We will use a similar approach to test the difference in the change between baseline and 6-month values of secondary outcomes (Specific Aim 2) and exploratory outcomes. In exploratory analyses, we will also test the difference in the change between baseline and 3-month values of outcomes (HbA1c, fasting glucose, systolic blood pressure, total-to-HDL cholesterol, body weight, insulin, HOMA-IR, diastolic blood pressure, waist circumference, and estimated CVD risk). We will also explore the use of mixed effects models to assess overall net change in HbA1c (by treating time as a linear variable) and other outcomes over the full study period. For each outcome, we will test modeling assumptions and will consider transformation of outcomes, if needed, to meet modeling assumptions. We will also perform sensitivity analyses using Markov-chain Monte Carlo techniques to impute missing values of the outcomes, using covariates for this imputation and will compare results from this analysis with our primary findings.

15. Anticipated Challenges

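### The two-laboratory weights for HbA1c change favour the laboratory with the larger variance, and the switch to DDL alone can be set off by an offset that cancels in change

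*Combined protocol and SAP*

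**What the plan says.** Section 13.B.2 makes the primary outcome depend on an agreement check: "We will use Bland-Altman plots to explore whether there is a systematic difference in HbA1c measured by LabCorp compared with DDL". If no systematic difference is found, "we will use the weighted average of change in HbA1c measures from the two labs as the outcome", with "weights defined as the ratio of the variance for each lab over the sum of the variance". Otherwise the rule is: "If we observe a systematic difference between HbA1c measured at LabCorp and DDL, we will use HbA1c measured at DDL". No visit, numerical limit or test defines a systematic difference.

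Section 10.B.5 gives the sampling. "HbA1c will be measured at LabCorp (Roche Tina Quant; fresh samples) from whole blood collected at screening, 3-month, and 6-month visits". The second assay is added for one purpose: "Following trial completion, to improve precision of HbA1c estimates, HbA1c will also be measured at the Diabetes Diagnostic Laboratory", on frozen samples "from whole blood collected at randomization, 3-month, and 6-month visits". Each laboratory therefore has its own baseline and its own 6-month value. Only DDL has a variant procedure: "Samples with Hb variants (C, D, E, S) that are measured at the Diabetes Diagnostic Laboratory will be reflexed" to a second method.

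**The concern.** **Weights (main point).** A weight proportional to a laboratory's variance rises with its noise. To minimise the variance of an average of two measurements with independent errors, the weight has to fall with the noise. The formula therefore works against the only stated reason for averaging. The reference attached to it, number 50, does not settle what was meant: that bibliography entry is a report on Mediterranean diets and metabolic syndrome.

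**Trigger (secondary point).** The check concerns HbA1c values, while the outcome is change formed within a laboratory. A constant offset between a fresh-sample immunoassay and a frozen-sample HPLC method would show on a Bland-Altman plot and could remove LabCorp, although it has no effect on the arm difference.

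What is at stake is the precision that the second assay was bought for.

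**Working it through.** **Inputs from the documents.** 142 analysed, so 71 per arm (Section 12, 1:1 allocation); two-sided alpha 0.05, unpaired t-test; SD of change 0.35; difference 0.17%. Section 12 also gives a preliminary SD of 0.28.

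**Assumptions.** The documents give no laboratory-specific variance. I assume error SDs of 0.10 and 0.15 per measurement, independent between laboratories and visits, and no slope difference.

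**1. The plan's own figure.** With 71 per arm and SD 0.35, the detectable difference at 80% power is 0.1657, which rounds to the 0.17 in Table 5. Power at 0.17 is 82.0%.

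**2. Direction of the weights.** Let k be the noisier laboratory's error variance divided by the other's. The written weight on the noisier laboratory is k/(1+k); inverse-variance weighting gives it 1/(1+k). In units of the more precise laboratory's error variance, the error variance of the average is
- as written: (k³+1)/(1+k)² = (k²−k+1)/(1+k)
- inverse-variance: k/(1+k)

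| k | written weight on noisier | written | inverse-variance | better laboratory alone |
|---|---|---|---|---|
| 1 | 0.50 | 0.50 | 0.50 | 1 |
| 1.5 | 0.60 | 0.70 | 0.60 | 1 |
| 2 | 0.67 | 1.00 | 0.67 | 1 |
| 4 | 0.80 | 2.60 | 0.80 | 1 |

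Setting the written expression to 1 gives k² = 2k, so above k = 2 the written average is worse than the better laboratory alone.

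**3. Power when both laboratories are kept.** Error variances of change are 2×0.10² = 0.020 and 2×0.15² = 0.045, so k = 2.25. The text does not say which variance enters the weights, so both readings follow.

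*Total variance of change.* If the more precise laboratory has SD 0.28, the true-change variance is 0.0784 − 0.020 = 0.0584 and the noisier laboratory's total is 0.1034 (SD 0.32). The written weight on it is 0.1034/(0.1034+0.0784) = 0.569. The average has variance 0.0584 + 0.569²×0.045 + 0.431²×0.020 = 0.0767, SD 0.277. Swapping the weights gives SD 0.271.

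*Error variance.* The weight on the noisier laboratory is 0.045/0.065 = 0.692, or 0.308 when inverted.

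| SDs of change | total: written / inverse | error: written / inverse | better laboratory alone |
|---|---|---|---|
| 0.32 and 0.28 | 95.3% / 96.1% | 94.0% / 96.3% | 94.9% |
| 0.35 and 0.31 | 90.3% / 91.1% | 88.6% / 91.4% | 89.6% |
| 0.38 and 0.35 | 82.7% / 83.4% | 80.9% / 83.9% | 82.0% |

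The loss is 0.7 to 0.8 points on the first reading, where the written average still beats the better laboratory alone. It is about 2 to 3 points on the second, where it does not.

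A wider contrast: more precise laboratory with SD 0.35 and error SD of change 0.10, k = 4. Error-variance weights give 77.1% as written, against 82.6% inverted and 82.0% for the better laboratory alone. Total-variance weights as written give 80.7%.

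**4. The trigger.** With a constant offset c, (y6 + c) − (y0 + c) = y6 − y0, so c drops out of change. As a stand-in for the undefined criterion, a paired t-test at 0.05 on simulated 6-month values (4,000 runs, 142 participants, error SD of change 0.10 in each laboratory) selected DDL alone in 65%, 100% and 100% of runs for offsets of 0.02, 0.05 and 0.10. The same test on change did so in about 5%. The estimated effect stayed at about −0.17 in both laboratories.

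Cost of dropping LabCorp when both SDs are 0.35:
- error SD 0.10: average variance 0.1225 − 0.020 + 0.010 = 0.1125, SD 0.335, power 85.1% against 82.0%, a loss of 3.1 points
- error SD 0.15: 0.1225 − 0.045 + 0.0225 = 0.100, SD 0.316, power 88.9%, a loss of 6.9 points

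**The case against.** The best defence is that nothing here damages the primary inference. That stands. A reader might infer that the rule biases the arm difference, inflates type I error or leaves the trial underpowered. The documents do not support this: the weights and the fallback affect only variance, and DDL alone meets the planned 80% if its SD is 0.35.

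Falling back to DDL is also partly defensible. The methods differ, one uses fresh and the other frozen samples, and only DDL re-tests variant samples. Proportional bias does not cancel, so some check is needed. If DDL is clearly the more precise laboratory, dropping LabCorp can gain power: in the first row of the table, 94.9% against 94.0% for the average with error-variance weights as written.

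The formula may be a slip for inverse-variance weights, since the sentence states a precision aim. That is plausible, but nothing in the text says so, and a literal programmer would implement the reverse.

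Two further inferences should be resisted. One is that 0.35 and 0.28 are the two laboratories' SDs: Section 12 gives them as a planning value and a preliminary trial value. The other is that the agreement check is distorted at baseline, because LabCorp's screening value set eligibility and DDL's baseline comes from a later draw. Section 13.B.2 never says that this pair will be used, and same-visit pairs exist at 3 and 6 months.

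**Conclusion.** The weight formula is wrong as written for its stated purpose. It does no harm only when the two variances are equal. Under the assumed errors of 0.15 and 0.10 per measurement it costs 0.7 to 0.8 power points with total variances and about 2 to 3 with error variances. At an error-variance ratio of 4 the loss under the second reading is about 5 points.

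The trigger is a smaller point. It can discard LabCorp for a difference that cancels, at a cost of about 3 to 7 points with equal SDs of 0.35 and error SDs of 0.10 to 0.15, and with a possible gain if DDL is clearly better. The two losses belong to alternative branches and do not add up.

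All sizes rest on assumed laboratory errors. Severity is low; the direction of the weights is certain, the size is not.

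**What to change.** 1. Replace the formula with w_i = (1/V_i) / (1/V_LabCorp + 1/V_DDL). State which variance V_i is, and estimate it pooled over arms. Equal weights are an acceptable simple alternative. Correct the reference.
2. Apply the Bland-Altman check to within-laboratory change or to proportional bias, not to a constant offset. Use the same-visit 3- and 6-month pairs pooled over arms, set the limit in advance, and state that the decision is made blind to arm. Section 7.C blinds investigators but does not mention this decision. For scale, a LabCorp slope of 0.90 or 1.10 moves an equal-weight average by 0.5 × 0.10 × 0.17 = 0.0085% at a true 0.17%. The study team should choose the limit.
3. Report DDL-only and LabCorp-only results as sensitivity analyses.

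The cost is wording in Section 13.B.2 and two extra model fits, with no new data. The downside is that slope bias below the limit stays in the average; the DDL-only analysis would help to show it.

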Our *long-term goal* is to develop and implement dietary intervention(s) that reduce risk of T2D. The *overall goal of this randomized controlled trial is to study the effect of a behavioral intervention promoting a low-carbohydrate/high-unsaturated fat and high-protein dietary pattern (initial target <40 g digestible carbohydrates, final target <60 g digestible carbohydrates) compared with a usual diet on metabolic risk factors among individuals with prediabetes or early-stage untreated diabetes (HbA1c 6.0–6.9%).* Specifically, we will test the following hypotheses:

Primary hypothesis: Compared with usual diet, over a 6-month period, a healthy low-carbohydrate/high unsaturated fat and high-protein dietary pattern will lead to a larger decrease of HbA1c, by at least 0.15%.

Secondary hypothesis: Over a 6-month period, a healthy low-carbohydrate/high-unsaturated fat and high-protein dietary pattern will lead to larger improvements in the following major secondary outcomes: fasting glucose, systolic blood pressure (BP), total-to-HDL-cholesterol ratio, and body weight.

Exploratory outcomes: We will also study the effect of the intervention on the 6-month change in: insulin and homeostasis model assessment of insulin resistance (HOMA-IR); diastolic BP; waist circumference; and estimated CVD risk.

To achieve these study aims, we will recruit 150 adults with prediabetes or untreated diabetes (HbA1c 6.0–6.9%) in the Greater New Orleans, LA area. Using a stratified, blocked randomization scheme, participants will be assigned to either a behavioral modification intervention aimed at promoting a healthy low-carbohydrate dietary pattern or to usual diet. The intervention group will have an intensive phase for 3 months, followed by a maintenance phase in months 4 through 6. The primary outcome will be difference between the active intervention and control groups in the change in HbA1c from baseline to 6 months of follow-up. We expect 80% power to detect a difference of at least 0.15% in change of HbA1c. Changes in other metabolic risk factors will be studied concurrently. Metabolic risk factors will be assessed at baseline, 3 months, and 6 months of follow-up.

There is much interest regarding dietary approaches to prevent T2D and its complications. The results from this study will help to determine whether, compared with usual diet, a behavioral intervention aimed at promoting a healthy low-carbohydrate dietary pattern improves metabolic risk factors.

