In the study on macronutrient composition of diet and risk factors for cardiovascular disease (MACRO) study, 148 individuals without clinical cardiovascular disease or diabetes and with obesity were randomly assigned to a low-carbohydrate or a low-fat behavioral dietary intervention for 12 months. In the low-carbohydrate arm, daily dietary intake of carbohydrates decreased from an average of 242 g at baseline to 97 g, 93 g, and 127 g at 3, 6, and 12 months, respectively. At 12 months, participants in the low-carbohydrate intervention group had greater decreases in weight (-3.5 kg; 95% CI, -5.6 to -1.4 kg) and fat mass (-1.5%; 95% CI, -2.6% to -0.4%) and greater improvement in several cardiovascular risk factors.³⁰ This suggests that restricting carbohydrates may be an option for weight loss and reduction of cardiovascular risk factors. Further analyses found that the low-carbohydrate dietary intervention led to similar or greater improvement in inflammation, adipocyte dysfunction, and endothelial dysfunction compared with the low-fat dietary intervention⁹² and that the low-fat diet reduced peptide YY more than the low-carbohydrate diet, suggesting satiety may be better preserved on low-carbohydrate diets.⁹³ No serious adverse events were reported in this study and the number of participants with symptoms were similar between the two diets, with the exception of more participants having headaches on the low-fat diet at 3 months (18 vs 6 participants, $p = 0.03$).³⁰ [name] served as PI for this study and [name] served as her mentor. [name] mentored one of her PhD students in conducting analyses and writing and editing manuscripts related to this project.

3.C. Other dietary intervention trial experience

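### The exploratory mixed model in 13.B.2 treats time as linear, although the intervention is front-loaded, and does not define the overall net change it is meant to estimate

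*Combined protocol and SAP*

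**What the plan says.** In section 13.B.2 the primary analysis is a linear regression on the baseline-to-6-month change in HbA1c, and the secondary outcomes follow a similar approach. Three further statements bear on this point:

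- The mixed model: an exploratory estimate of overall net change in HbA1c, fitted "by treating time as a linear variable", with an extension to other outcomes across the whole study. The parenthesis on linear time is attached to HbA1c; whether it also covers the other outcomes is unclear. Random effects, covariance, handling of baseline and the time-by-arm term are not given, and overall net change is not defined.
- A separate month-3 analysis among the exploratory analyses: "we will also test the difference in the change between baseline and 3-month values of outcomes", with HbA1c on the list.
- Model checking: "For each outcome, we will test modeling assumptions and will consider transformation of outcomes, if needed, to meet modeling assumptions". No remedy other than transformation is named.

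On design, section 1 says "Metabolic risk factors will be assessed at baseline, 3 months, and 6 months of follow-up" and "The intervention group will have an intensive phase for 3 months, followed by a maintenance phase in months 4 through 6". Section 8.A puts 8 of the 11 in-person sessions in the first three months (4 individual, 4 group) and 3 in months 4 to 6. Section 2.I notes that HbA1c averages glucose over 8 to 12 weeks. For the low-carbohydrate arm of the predecessor trial, section 3.B gives one baseline figure and three follow-up figures (months 3, 6 and 12, in that order): "daily dietary intake of carbohydrates decreased from an average of 242 g at baseline to 97 g, 93 g, and 127 g".

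**The concern.** A line through 0, 3 and 6 months allows only one shape of treatment effect: half of it at month 3 and all of it at month 6. The documents point towards an earlier response. Contact is concentrated in the first three months, the HbA1c window fits inside that period, and intake in the predecessor trial was nearly flat from month 3 to month 6. If HbA1c behaves similarly, the line does not describe the data.

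At stake is what the model can report. Depending on how overall net change is read, it either repeats the primary contrast or gives an average that is too small. The planned assumption checks may reveal the misfit, but transforming the outcome is not a direct remedy for a wrong time shape.

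**Working it through.** **Inputs.** The plan gives no numerical target for the mixed model. I take d = 0.17 and an SD of change of 0.35 from section 12. These agree with each other: 71 per arm, two-sided 0.05 and 80% power give a detectable difference of 0.166, which rounds to 0.17. Let f be the share of the 6-month effect present at month 3. The documents give no 3-month HbA1c effect, so f is an assumption, varied from 0.5 to 1.25. One anchor is intake in the predecessor trial: (242 − 97)/(242 − 93) = 145/149 = 0.97.

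**1. The slope with complete data.** The between-arm differences are 0, f·d and d. With time centred at −3, 0 and 3, slope = (−3·0 + 0·f·d + 3·d)/18 = d/6. So 6 × slope = d = 0.17 for every f, and month 3 has zero weight. Generalised least squares gives the same ratio of 1.00 under compound symmetry, random intercept and slope, and AR(1), with arm-specific intercepts. It is not universal: one illustrative unstructured covariance with variance rising over time gave 1.13 at f = 1.

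**2. Implied month-3 change and average over the two follow-up visits.** The line always gives 0.5d at month 3 and (0.5 + 1)/2 = 0.75d on average. The true values are f·d and (f + 1)/2·d.

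| f | error at month 3 | true average | error in average |
|---|---|---|---|
| 0.50 | 0% | 0.750d | 0% |
| 0.67 | −25% | 0.835d | −10% |
| 0.80 | −37.5% | 0.900d | −17% |
| 0.90 | −44% | 0.950d | −21% |
| 0.97 | −48% | 0.985d | −24% |
| 1.00 | −50% | 1.000d | −25% |
| 1.25 | −60% | 1.125d | −33% |

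These errors are for change from baseline. If the gap between the fitted lines is read instead, at f = 1 it is 0.113 at month 3 (−33%) and 0.198 at month 6. The mean is 0.156 against 0.170, or −8%, with a spurious baseline gap of 0.028.

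**3. Dropout after month 3, f = 1.** A person seen only at 0 and 3 months contributes a 6-month extrapolation of 2·f·d. Within-person information on the slope is 18 for three visits and 4.5 for two, so at dropout m such people carry weight of about 4.5m/[18(1 − m) + 4.5m].

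- m = 0.05: 0.225/17.325 = 1.3%
- m = 0.10: 0.45/16.65 = 2.7%
- m = 0.20: 0.9/15.3 = 5.9%

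Generalised least squares under compound symmetry (correlation 0.5 to 0.85) gives slightly less: 1.2 to 1.3%, 2.4 to 2.6% and 5.3 to 5.7%. At 5% dropout the bias is about 0.002, against a standard error of 0.35 × √(2/71) = 0.059.

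**4. Common baseline, no dropout, f = 1.** If the arms are forced to share a baseline mean, 6 × slope is 1.09d at correlation 0.5, 1.05d at 0.7 and 1.03d at 0.85 under compound symmetry. The plan neither specifies nor excludes this.

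**5. Cost of categorical visit (75 per arm, compound symmetry).** The standard error of the 6-month contrast is 0.35 × √(2/75) = 0.057 under both linear and categorical time. The two-visit average has variance 1.5σ²(1 − ρ) against 2σ²(1 − ρ) for a single change, so its standard error is 0.057 × √0.75 = 0.050.

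**The case against.** The strongest reply is that nothing confirmatory depends on this model. It is labelled exploratory, and the primary test, the secondary tests and the sample size do not use it. That stands.

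A reader might infer that the model cannot deliver the net change at all. The documents do not support this. Section 3.C uses net change for a difference in change over a study, and on that reading the slope returns the 6-month value exactly under the conditions in step 1.

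A reader might also infer that the trial will misreport its 3-month effect by about half. That is not supported either. The 3-month change is tested directly in the preceding sentence of 13.B.2, and the half applies only when f is close to 1. The 97% figure is carbohydrate intake, in one arm, in people with obesity and without diabetes. It is neither HbA1c nor a between-arm effect, and HbA1c need not follow the intake curve.

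Finally, with complete data and arm-specific baselines, a categorical model's 6-month contrast also takes nothing from month 3. That is true, but the categorical model estimates the 3-month contrast and the average without imposing a shape on them.

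**Conclusion.** The point holds as a specification weakness in an exploratory analysis. Linear time imposes a 1:2 ratio of effects that the plan's own design gives no reason to expect, and the target quantity is undefined. Read as the 6-month change, the model repeats the primary contrast. Read as the average follow-up effect, it is about 24% low at f = 0.97, 10% low at f = 0.67 and correct at f = 0.5.

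Upward bias in the 6-month estimate under a plateau is about 1% at the planned 95% follow-up and about 2.5% at 10% dropout. It is larger, about 5 to 9% without dropout, if a common baseline is modelled with correlation 0.5 to 0.7, and it can also be larger under strongly unequal variances. All these sizes rest on the assumed f, and those with dropout or a common baseline also on an assumed covariance. It would be wrong to conclude that the primary, secondary or separate 3-month results are at risk.

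**What to change.** In 13.B.2, replace linear time with visit as a categorical factor (0, 3 and 6 months), visit-by-arm terms and an unstructured covariance. State how baseline is handled. Define overall net change as the average of the 3- and 6-month between-arm contrasts, and report it alongside each of the two. Say whether the same model applies to the other outcomes.

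The cost is a few lines of text and one extra mean parameter per arm. No further data are needed, and the change in the standard error of the 6-month contrast is negligible: none with arm-specific intercepts (0.057 under both), and 0.0486 against 0.0494 with a common baseline. It should be settled before outcome data are analysed by arm.
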